1. SCHEDULE OF ASSESSMENTS

All participant enrolled will form part of the main study. Main study assessments, questionnaires, and procedures may be performed or administered in any order. Specific sub-study questionnaires and assessments are detailed in Sections 7.2 and in the sub-study-specific plans.

Procedure / assessment / questionnaire	Main Study			Sub-Study(ies)	
	Day 1 (+28 ¹)			Day 2 to 180 (+28 ¹)	
	Screening	Baseline	FU#1	Sub-Study	FU#2
Informed consent ²	X				
SARS-CoV-2 infection and vaccination history ³	X				
Main study eligibility review	X				
Demographic data		X			
Medical and surgical history ⁴		X			
Long-COVID symptom-directed history ⁵		X			
Previous and concomitant medications ⁶		X			
Symptom-directed physical examination ⁷		X			
Vital signs ⁸		X			
Psychological and Somatic Symptoms of COVID-19 Survey		X			
Headache Impact Test-6 (HIT-6)		X			
Patient Health Questionnaire-9 (PHQ-9)		X			
Generalised Anxiety Disorder 7-item (GAD-7)		X			
PTSD Checklist – Civilian Version (PCL-C)		X			
Mood Disorder Questionnaire (MDQ)		X			
Montreal Cognitive Assessment (MOCA)		X			
Daily Fatigue Impact Scale (D-FIS)		X			
COVID-19 Related Stress Survey		X			
Multidimensional Scale of Perceived Social Support (MSPSS)		X			
Perceived Stress Scale-10 (PSS-10)		X			
Adverse Childhood Experiences (ACEs) Questionnaire		X			
Normal Activities and Work Productivity Questionnaire		X			
Pittsburgh Sleep Quality Index (PSQI)		X			
Epworth Sleepiness Scale (ESS)		X			
Berlin Questionnaire		X			
International Restless Legs Syndrome Study Group Severity Rating Scale (IRLS)		X			
Sleep quality and mood visual analogue scale		X			
Brief Pain Inventory (BPI)		X			
Modified MRC Dyspnoea Scale		X			
Six-minute walk test (distance)		X			
ECG ⁹		X			
Blood sample for laboratory tests ¹⁰		X			
Blood and urine sample storage ¹¹		X			
Optional HIV test		(X)			
Selection of participants for sub-study(ies) ¹²		X-----X			

Procedure / assessment / questionnaire	Main Study			Sub-Study(ies)	
	Day 1 (+28 ¹)			Day 2 to 180 (+28 ¹)	
	Screening	Baseline	FU#1	Sub-Study	FU#2
Telephonic follow-up			X ¹³		X ¹⁴
Sub-study informed consent				X ¹⁵	
Participation in one, or more, sub-study				X-----X	
Collection of adverse event data ¹⁶		X		X	

FU#1/2 = Telephonic follow-up number 1 or 2; ECG = electrocardiogram; HIV = human immunodeficiency virus

- 1 Time window for the follow-up telephonic contact is +28 days from completion of the assessments for the relevant part of the study.
- 2 Written or electronic informed consent to be provide prior to any screening or study-specific assessments, questionnaires or procedures are conducted.
- 3 Including dates of diagnosis through SARS-CoV-2 PCR or antigen testing, or date of positive antibody testing, COVID-19 vaccination dates (if administered), COVID-19 hospitalisation dates (if applicable).
- 4 Including information related to specific risk factors associated with poor COVID-19 outcomes and a detailed history of previous COVID-19 episodes (if applicable).
- 5 Targeting symptoms not covered in other administered surveys and questionnaires.
- 6 Details regarding previous and concomitant medications from the time of the participant's confirmed SARS-CoV-2 infection will be collected.
- 7 Including height and weight, and at least a general, cardiorespiratory, and skin examination and other systems as indicated through reported symptoms.
- 8 Vital signs (blood pressure, pulse rate, respiratory rate, body temperature, and SpO₂) will be measured after 5 min resting.
- 9 A standard 12-lead ECG will be conducted after the participant has rested in the supine position for 10 minutes.
- 10 A blood sample will be collected for full blood count, serum chemistry, liver function, renal function, glucose, HbA1C, and inflammatory markers assessments, and for DNA extraction for genotyping and sequencing.
- 11 Blood (50 mL) and urine (100 mL) samples will be stored for possible future analysis pending emerging information.
- 12 Study team personnel will review each participant's baseline data and identify participants with and without Long-COVID who are eligible for participation in one, or more, sub-study. Invited participants will be randomly selected from the set of eligible participants for each sub-study. Participants who decline the invitation to participate in one, or more, sub-study, will be replaced by a randomly selected, matched-cohort participant where possible.
- 13 Participants will be contact telephonically to inform them of the results of their baseline assessments, and to arrange for follow-up clinical consultations as required for any identified medical or mental health issues. Participants that have been selected for sub-study participation will be invited to return for consent and enrolment into these sub-studies.
- 14 Participants will be contact telephonically to inform them of the results of their sub-study assessments, and to arrange for follow-up clinical consultations as required for any identified medical or mental health issues.
- 15 Written or electronic informed consent to be provide prior to any sub- study-specific assessments, questionnaires or procedures are conducted.
- 16 Adverse events associated with study assessments or procedures will be recorded in the eCRF for each participant.

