7.1.3 Telephonic follow-up (up to 28 days after completion of baseline visit)

Participants will be contacted telephonically within 28 days of completion of their baseline visit to inform them of the results of their assessments. Abnormalities detected in assessments (suggesting undiagnosed medical or mental health issues) will be managed by on-study medical personnel with referral as appropriate.

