8.2 Adverse Events

8.2.1 Definitions

Some of the assessments and procedures used in this study may be associated with rare discomfort or adverse events (AEs), e.g., blood sampling, six-minute walk test, injection of contrast media, skin irritation from electrodes used in polysomnography.

For this study, AEs associated with study assessments or procedures will be recorded in the eCRF for each participant. The following information be recorded for each AE:

- a description of the AE
- the dates of onset and resolution of the event
- the characteristics of the event (seriousness, severity in accordance with CTCAE Version 5.0, Nov 2017 [43])
- the action taken in response to the event (including treatment required)
- the outcome of the event.

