9.2.3 Safety data

All AEs will be listed.

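### Neither follow-up call includes an adverse event enquiry, so procedure-related events that start or stay open after a participant's last visit have no scheduled collection point

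*Protocol*

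**What the plan says.** The schedule in Section 1 of the protocol has five columns: Screening, Baseline, FU#1, Sub-Study and FU#2. The row "Collection of adverse event data" carries a mark under Baseline and one under Sub-Study. The row "Telephonic follow-up" carries marks under FU#1 and FU#2.

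Note 16 to the schedule sets the scope: "Adverse events associated with study assessments or procedures will be recorded in the eCRF for each participant". It gives no start or end of collection.

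Section 8.2.1 lists what is recorded for each AE. The list includes "the dates of onset and resolution of the event" and "the outcome of the event". Among the possible sources of AEs it names blood sampling, the six-minute walk test, contrast injection and "skin irritation from electrodes used in polysomnography".

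Section 7.1.3 describes the first call: "Participants will be contacted telephonically within 28 days of completion of their baseline visit to inform them of the results of their assessments". Section 7.2.3 describes the second call in the same way for sub-study results, and adds that feedback from the overnight sleep study may come as late as 6 months after that night. Notes 13 and 14 and Section 6 give the calls the same purposes: reporting results, arranging consultation or referral and, at FU#1, inviting selected participants to sub-studies.

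Section 9.2.3 gives the whole planned safety output: "All AEs will be listed".

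**The concern.** The protocol asks for data that its own schedule does not provide a way to collect. A resolution date and an outcome can be entered at the visit only if the event has ended by the time the participant leaves. Some of the effects named in Section 8.2.1, such as skin irritation under electrodes, can plausibly appear or persist after that. A planned contact follows each part of the study, yet site staff working from the schedule are not told to use it for this purpose.

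What is at stake is the completeness of the AE listing. Events seen during a visit will be captured more fully than events that emerge later, and entries for events open at the last visit may lack a resolution date or outcome.

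**Working it through.** The protocol states no figure for this point, so there is none to reproduce. The check sets the relevant places side by side and then counts who is affected.

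**1. Column positions.** The table was read from a PDF, so the marks could have shifted. Two other rows fix the columns. The telephone row falls under FU#1 (note 13) and FU#2 (note 14), and the sub-study consent row falls under Sub-Study (note 15). Read against these, the two AE marks belong to Baseline and Sub-Study, and both call columns are empty.

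**2. Whether the text fills the gap.**

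| Place | Purpose given to the call | AE enquiry named? |
|---|---|---|
| Note 13 (FU#1) | Baseline results, consultations, sub-study invitation | No |
| Note 14 (FU#2) | Sub-study results, consultations | No |
| Section 6 | Results; management or referral of abnormal findings | No |
| Section 7.1.3 (FU#1) | Results; management or referral | No |
| Section 7.2.3 (FU#2) | Results; management or referral | No |

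The text therefore agrees with the table. Nor does the protocol state an AE collection period or a rule for following open events to resolution.

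**3. Against the data required.** Section 8.2.1 requires onset date, resolution date and outcome. For an event that starts and ends within a visit, the schedule supplies all three. For an event open at the last visit, it supplies the onset only. For an event that starts after the last visit, it supplies none.

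**4. Who has a single collection point.** Inputs: 400 participants in four cohorts of 100, and up to 30 per cohort in each sub-study (Synopsis, Sample Size; Sections 6 and 7.2); six sub-studies (Section 4.1).

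- Maximum per sub-study: 30 × 4 = 120.
- If the same participants filled all six sub-studies: 400 − 120 = 280 would have baseline as their only AE collection point.
- If the sub-studies overlapped little: 6 × 30 = 180 places per cohort of 100, which is enough for every participant to be in at least one, so the number could fall to 0.
- If sub-study places are not filled, the number could exceed 280.

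The number of main-study-only participants is thus not fixed by the protocol. In every case, the time after a participant's own last visit has no scheduled AE enquiry.

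**5. Timing of the existing calls.** Both calls fall within 28 days of the relevant last assessment, except that feedback to sleep sub-study participants may wait until 6 months after the overnight recording. Adding an AE question to the feedback call alone could therefore come very late for electrode irritation, one of the protocol's own examples.

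**The case against.** The strongest reply is that nothing ends AE collection when the participant leaves. Note 16 and Section 8.2.1 require procedure-related AEs to be recorded without a time limit, so leaving the resolution or outcome of an open event blank would breach the protocol rather than follow it. An event that a participant volunteers during a call can be recorded. This stands. A reader might infer that delayed events are lost, or that the listing will hold on-the-day events only, but the documents support only that no enquiry is scheduled.

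Second, later contacts exist for some participants. The cardiac sub-study has up to three visits, some respiratory participants may be followed for a further 3 to 6 months, and a participant may be in several sub-studies. Delayed baseline events, or events between sub-study visits, can be picked up there. The sub-study plans, which are not shown, may add more. This also stands, and it limits the gap to the time after each participant's last visit. Plans for sub-study procedures would not be expected to govern FU#1 for someone in no sub-study.

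Third, exposure differs. Polysomnography belongs to the sleep sub-study, not the main study, whose procedures mostly have immediate effects. The protocol does not say which procedure uses contrast, so no contrast-exposed number can be derived. It would therefore be wrong to apply one figure, such as all 400 participants with a 28-day gap, to every risk that Section 8.2.1 names.

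Fourth, the study is observational, gives no treatment, and has no objective concerning the tolerability of its procedures. A reader might infer that the study fails to describe tolerability, or that delayed events do not reach the Medical Monitor. The first is not an aim of the study. The second has no support: Section 8.1.3 gives the Medical Monitor review of safety information under a Monitoring Plan that is not shown.

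**Conclusion.** The point holds in a limited form. The schedule places AE collection at Baseline and Sub-Study only and no text adds it to either call, while Section 8.2.1 requires items that for some events can be known only later. Events starting or remaining open after a participant's last visit have no scheduled collection point, and the listing may be incomplete for them.

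The size is minor. Only procedure-related AEs are recorded, Section 8.2.1 itself describes them as rare, they are only listed, and no primary or secondary endpoint depends on them. The number of events affected cannot be estimated from the protocol.

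The conclusion assumes that the table columns were read correctly, which the neighbouring rows support, and that no sub-study plan or manual outside the protocol adds an AE question to the calls. If one does, the protocol's schedule should still be brought into line with it.

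**What to change.** 1. Mark the AE row under FU#1 and FU#2 in the Schedule of Assessments.
2. In Sections 7.1.3 and 7.2.3 and in notes 13, 14 and 16, have each call ask about any event since the study procedures and update the resolution date and outcome of events still open.
3. State the collection period: from the first study procedure to the follow-up call for that part of the study.
4. For sleep sub-study participants, state that the AE enquiry still takes place within the 28-day window even when feedback on results comes later.

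The cost is one or two questions in calls already planned, minor protocol wording, an eCRF page for the call, and a few more listed AEs. Sleep participants may need a short call separate from their feedback. No visit is added.

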Background	
“Long-COVID” (also known as post-COVID-19 syndrome, post-acute sequelae of COVID-19, or chronic COVID syndrome, used here as ‘Long-COVID’ for brevity), is a complex array of postconvalescence symptoms following SARS-CoV-2 infection. The syndrome, common in COVID-19 survivors, can affect every organ system through as-yet uncharacterised but presumed immunological mechanisms. Prevalence depends on the definition used and time-period of follow-up, as well as the population being studied. The syndrome has been associated with significant and persistent disability in some survivors but has been hampered, until recently, by lack of a clinical definition, diagnostic criteria, and objective measures of disease or disability [1]. A Delphi-informed initial WHO clinical definition was released in early October 2021 but has attracted much criticism from both clinicians and survivors for a host of reasons, ranging from a lack of precision to a lack of inclusion [2].
 
Further complicating the syndrome is the context in which the SARS-CoV-2 epidemic occurred, which was associated with severe lockdowns in many countries (including South Africa) with social isolation, widespread fear and disinformation, widespread economic hardship, and loss of family and acquaintances, all of which contribute to symptoms (psychiatric and sleep disturbances, pain, and other syndromes) reported to be associated with Long-COVID. Finally, many Long-COVID symptoms overlap with those seen in patients hospitalised for any severe illness, especially those admitted to intensive care and ventilated. However, the proliferation of literature reporting associations of Long-COVID symptoms with more severe COVID-19 disease, and objective immunological, radiological, and organ-specific dysfunction in those reporting symptoms, suggests that the entity is real. The pathogenesis of Long-COVID is poorly understood, but this association with more severe disease - where immune dysregulation plays a major role in those with hospitalization, respiratory failure, and death - suggests an immune-mediated inflammatory dysfunction that may impact all organs [3-14].
 
The sheer rapidity of four major infection waves in South Africa, the initial focus on containing the hospital burden of those with severe illness, and subsequent emphasis on the roll-out of a mass vaccination program, has left little space for studying SARS-CoV-2 sequelae in survivors. This group, loosely and inaccurately termed “recovered” in South African reporting, were largely unvaccinated or partly vaccinated at the time of infection, leaving them at risk of developing Long-COVID.
 
Long-COVID reported symptoms are extraordinarily broad. Over 50 symptoms were reported in a recent review, with over 80% of COVID-19 survivors having at least one symptom after infection [4]. The diagnosis is one of exclusion, and symptoms may fluctuate although tend to resolve with time. It is unclear whether disability and organ damage may be permanent in some patients. No specific treatment exists, and interventions are typically symptom-directed. SARS-CoV-2 vaccination appears to benefit many symptomatic survivors [15]. At the time of writing, no African data characterising the clinical features of Long-COVID have been published.

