Design	
This is a single centre, follow-up, observational, cross-sectional study of four distinct, longitudinal cohorts. Extensive clinical history will be obtained from each participant, and symptom questionnaire characterisation of Long-COVID (with a strong focus on organ-specific dysfunction, psychiatric, sleep, and pain parameters – all of which appear to be major features of Long-COVID), as well as laboratory and genetic characterisation will be performed. A subset of each cohort will be randomly selected for more specific syndrome characterisation related to sleep and pain, respiratory, cardiology, renal and glucose metabolism.
 
The consequences of Long-COVID will be described and compared in four large, well-described clinical cohorts of African patients surviving SARS-CoV-2:
 
• Cohort 1: asymptomatic subjects found to be PCR/antigen/antibody-positive during routine screening for SARS-CoV-2 infection• Cohort 2: symptomatic outpatients who were confirmed to have COVID-19 through a positive PCR/antigen test• Cohort 3: inpatients surviving hospitalisation for severe COVID-19 and who were PCR/antigen-positive• Cohort 4: participants vaccinated in clinical trials in 2020 prior to widespread community exposure to SARS-CoV-2, and hence protected from severe COVID-19 (and possibly Long-COVID) if subsequently infected. 
After obtaining informed consent from potential participants, a single cross-sectional, baseline visit will be conducted for each participant. Demographic data, clinical history (including COVID-19 history, targeted symptoms, and risk factors), COVID-19 vaccination dates (if administered), and details of previous and concomitant medications will be collected. Multiple questionnaires related to psychiatric screening, psychosocial factors, work function assessment, sleep quality, and pain assessment will be administered. Respiratory and cardiac function will be evaluated through a dyspnoea scale, walking test and an electrocardiogram (ECG). Laboratory evaluations will include a full blood count, serum chemistry, liver function tests, renal function assessment, inflammatory markers, and DNA extraction for genotyping. Blood and urine samples will be stored locally for possible future analysis. HIV testing will be performed for participants consenting to this optional assessment.
 
After the baseline visit, participants with Long-COVID will be identified using the WHO clinical definition and general health assessments [2]. Randomly selected sub-groups of participants with, and without, Long-COVID will be selected from each of the four cohorts for additional investigations through participation in the following sub-studies:
 
• Respiratory evaluation: dyspnoea assessment, high-resolution CT scan, lung function studies including spirometry and diffusion capacity (DLCO)• Cardiac evaluation: clinical history and examination, serial blood pressure, six minute walk test (distance), ECG, echocardiogram including speckle tracking, cardiac magnetic resonance imaging (MRI), creatine kinase MB fraction (CK-MB), cardiac troponin T (cTnT), prohormone brain natriuretic peptide (pro-BNP), and possible

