2. INTRODUCTION

2.1 Background

“Long-COVID” (also known as post-COVID-19 syndrome, post-acute sequelae of COVID-19, or chronic COVID syndrome, used here as ‘Long-COVID’ for brevity), is a complex array of postconvalescence symptoms following SARS-CoV-2 infection. The syndrome, common in COVID-19 survivors, can affect every organ system through as-yet uncharacterised but presumed immunological mechanisms. Prevalence depends on the definition used and time-period of follow-up, as well as the population being studied. The syndrome has been associated with significant and persistent disability in some survivors but has been hampered, until recently, by lack of a clinical definition, diagnostic criteria, and objective measures of disease or disability [1]. A Delphi-informed initial World Health Organisation (WHO) clinical definition was released in early October 2021 but has attracted much criticism from both clinicians and survivors for a host of reasons, ranging from a lack of precision to a lack of inclusion [2].

Further complicating the syndrome is the context in which the SARS-CoV-2 epidemic occurred, which was associated with severe lockdowns in many countries (including South Africa) with social isolation, widespread fear and disinformation, widespread economic hardship, and loss of family and acquaintances, all of which contribute to symptoms (psychiatric and sleep disturbances, pain, and other syndromes) reported to be associated with Long-COVID. Finally, many Long-COVID symptoms overlap with those seen in patients hospitalised for any severe illness, especially those admitted to intensive care and ventilated. However, the proliferation of literature reporting associations of Long-COVID symptoms with more severe COVID-19 disease, and objective immunological, radiological, and organ-specific dysfunction in those reporting symptoms, suggests that the entity is real. The pathogenesis of Long-COVID is poorly understood, but this association with more severe disease - where immune dysregulation plays a major role in those with hospitalization, respiratory failure, and death - suggests an immune-mediated inflammatory dysfunction that may impact all organs [3-14].

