2.2 Long-COVID

[figure not shown]

Figure 1: Long-term effects of coronavirus disease 2019 (COVID-19). The meta-analysis of the studies included an estimate for one symptom or more reported that 80% of the patients with COVID-19 have long-term symptoms.

CRP = C-reactive protein, CT = computed tomography, IL-6 = Interleukin-6, NT-proBNP = (NT)-pro hormone BNP, OCD = Obsessive Compulsive Disorder, PTSD = Post-traumatic stress disorder.

This figure was created using Biorender.com (Reproduced under a Common Creation Licence, from Lopez-Leon, S., Wegman-Ostrosky, T., Perelman, C. et al [4])

Long-COVID reported symptoms are extraordinarily broad. Over 50 symptoms were reported in a recent review, with over 80% of COVID-19 survivors having at least one symptom, sign, or abnormal

laboratory parameter after infection [4]. Fatigue (58%), headache (44%), attention disorder (27%), hair loss (25%), and dyspnoea (24%) were the most reported symptoms in this review, with abnormal chest x-ray or computed tomography (CT) scan findings detected in 34% of patients. Other symptoms and signs were related to lung disease (cough, chest discomfort, reduced pulmonary diffusing capacity, sleep apnoea, and pulmonary fibrosis), cardiovascular disorders (arrhythmias, myocarditis), neuropsychiatric diseases (dementia, depression, anxiety, obsessive-compulsive disorders), and others were non-specific such as tinnitus and night sweats.

The diagnosis of Long-COVID is one of exclusion, and symptoms may fluctuate although tend to resolve with time. It is unclear whether disability and organ damage may be permanent in some patients. No specific treatment exists, and interventions are typically symptom-directed. SARS-CoV-2 vaccination appears to benefit many symptomatic survivors [15].

At the time of writing, no African data characterising the clinical features of Long-COVID have been published.

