7.1.2.2 Medical and surgical history

In addition to general information related to past and current relevant medical conditions and surgical procedures, and menstrual cycle, pregnancy and lactation status (for female participants only), the following specific information will be collected:

- COVID-19 history (for participants with previous symptomatic infection(s)) including:
 - Symptoms experienced (including cough, fatigue, fever, malaise, shortness of breath, ageusia, anosmia, and other symptoms)
 - Whether or not the participant was pregnant at the time of SARS-CoV-2 infection (female participants only)
 - Whether or not the participant required supplemental oxygen at the time of COVID-19
 - Whether or not the participant required intensive care unit (ICU) admission for COVID-19 (Cohort 3 only)
 - Whether or not the participant required mechanical ventilation for COVID-19 (Cohort 3 only)
- Long-COVID symptom-directed history to gather information about symptoms not assessed through the detailed questionnaires and surveys listed in Sections 7.1.2.5 to 7.1.2.6.

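### Study staff assign Long-COVID status from records that show cohort, hospitalisation and vaccination, so classification error can differ between cohorts in an unknown direction

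*Protocol*

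**What the plan says.** Two places govern how status is assigned. The Synopsis (Design) and section 4.1 give the criterion: "participants with Long-COVID will be identified using the WHO clinical definition and general health assessments". No item list, threshold or rule for combining the two parts follows. Footnote 12 to the Schedule of Assessments says who does it and from what: "Study team personnel will review each participant's baseline data and identify participants with and without Long-COVID". That footnote belongs to the row on choosing sub-study participants, so it is best read together with section 4.1.

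The record under review reveals the cohort. Footnote 3 lists "COVID-19 vaccination dates (if administered), COVID-19 hospitalisation dates (if applicable" among the screening data. Section 7.1.2.2 includes "Whether or not the participant required intensive care unit (ICU) admission for COVID-19 (Cohort 3 only", and ventilation is handled in the same way. Section 6 sets sub-study numbers per cohort, so the selecting team needs to know the cohort anyway.

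The protocol itself describes room for judgement. Section 2.2 says "The diagnosis of Long-COVID is one of exclusion", and section 2.1 reports criticism of the WHO definition "ranging from a lack of precision to a lack of inclusion".

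It also writes down expectations. Section 2.1 links Long-COVID symptoms with more severe acute disease. Section 4.1 describes Cohort 4 as "hence protected from severe COVID-19 (and possibly Long-COVID) if subsequently infected".

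Section 4.1 plans to compare the four cohorts. Section 9.2.2 summarises primary and secondary endpoints by cohort and by disease status. Section 3 sets Long-COVID participants against controls from the same cohorts. No section hides cohort from the people who classify, or provides a second reader.

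**The concern.** Three conditions meet at one step: a decision that needs judgement, a visible exposure group, and a written expectation about that group. Together they allow sensitivity and specificity of the classification to differ between cohorts. Two cohorts with the same true frequency could then show different observed frequencies.

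Status is also used downstream. It divides the endpoint summaries, and it determines who can be drawn as a case or a control in the six sub-studies of section 4.1. That draw happens during the study, so an SAP written for the analysis cannot undo it.

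**Working it through.** **Inputs from the protocol.** 100 participants per cohort, 400 in all (Synopsis, Sample Size). No sample size calculation, frequency of Long-COVID or error rate is stated, so there is no planned figure to reproduce.

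**Assumed inputs.** The true frequency p is the same in both cohorts. Sensitivity (Se) and specificity (Sp) of the staff classification differ by cohort. All Se and Sp values below are assumptions, used to show scale.

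**Formula.** Observed frequency = p × Se + (1 − p) × (1 − Sp).

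**Step 1: p = 0.30 in cohorts A and B.**

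| Case | Se/Sp in A | Se/Sp in B | Observed in A | Observed in B | Spurious difference |
|---|---|---|---|---|---|
| Mild | 0.88/0.92 | 0.84/0.95 | 0.264 + 0.056 = 0.320 | 0.252 + 0.035 = 0.287 | 3.3 points |
| Middle | 0.90/0.90 | 0.80/0.97 | 0.270 + 0.070 = 0.340 | 0.240 + 0.021 = 0.261 | 7.9 points |
| Strong | 0.95/0.85 | 0.75/0.98 | 0.285 + 0.105 = 0.390 | 0.225 + 0.014 = 0.239 | 15.1 points |

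With p from 0.20 to 0.40 the range is 3.2 to 15.8 points. Swapping A and B reverses the sign.

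**Step 2: scale.** The 95% half-width for a difference between two cohorts of 100 at p = 0.30 is 1.96 × √(2 × 0.30 × 0.70 / 100) = 0.127. The mild and middle cases lie inside it; the strong case exceeds it. Being inside does not make a bias harmless, because it shifts the estimate and the interval does not show it.

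**Step 3: a second set of assumptions.** Take an average of 0.90/0.90, moved in opposite directions in the two cohorts, with p from 0.20 to 0.80. The last column is the chance that a two-sided 5% test of two proportions would declare a difference. The protocol plans no such test; the column only shows scale.

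| Se/Sp in A v B | Spurious difference | Chance of a false difference |
|---|---|---|
| 0.90/0.90 v 0.90/0.90 | 0 points | 5% |
| 0.925/0.875 v 0.875/0.925 | 5 points | 11–13% |
| 0.95/0.85 v 0.85/0.95 | 10 points | 30–36% |
| 1.00/0.80 v 0.80/1.00 | 20 points | 82–90% |

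The first row is what equal error rates would give: the labels are still imperfect, but no cohort difference is created.

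**Step 4: within one cohort.** If the error does not depend on the test result given true status, a case-control mean difference shrinks by the factor PPV + NPV − 1. For the middle case:

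- A: 0.270/0.340 + 0.630/0.660 − 1 = 0.794 + 0.955 − 1 = 0.75.
- B: 0.240/0.261 + 0.679/0.739 − 1 = 0.920 + 0.919 − 1 = 0.84.

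The contrast is diluted, not created, and by different amounts in the two cohorts.

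**Step 5: pooled over the two cohorts.** In the middle case, cohort A supplies 34.0 of 60.1 labelled cases (57%) and 66.0 of 139.9 labelled non-cases (47%), where the truth is half of each. An unadjusted pooled summary by status then picks up part of any real difference between the cohorts.

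**The case against.** Four points against the concern carry weight.

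- **The primary endpoint is not the staff label.** A reader might infer that the label determines the primary result. Section 3 words that endpoint as the occurrence, severity and duration of symptoms, and sections 7.1.2 to 7.1.2.6 collect symptoms largely with standardised questionnaires. Status reaches it only through the split by status, any per-cohort proportion with Long-COVID, and the choice of which symptoms count.
- **The direction is open.** A reader might infer that bias must favour what the protocol expects: more Long-COVID after hospitalisation, less after vaccination. Section 2.1 also says the symptoms overlap with those after any severe hospital illness, above all after intensive care. Under a diagnosis of exclusion, a reviewer who sees an ICU stay might decide against Long-COVID.
- **Much is recoverable.** A reader might infer that no later analysis could help. Item-level answers and dates are kept for everyone, so main-study status can be re-derived by a fixed rule. Only the sub-study sampling cannot be redone.
- **Simple masking has its own cost.** Removing hospital and ICU history from a judgement of exclusion removes a leading alternative explanation, and could itself add error in Cohort 3.

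The WHO definition is a named criterion and limits discretion, and an operational rule may stand in the SAP or the Study Assessments Manual, neither of which is at hand. That softens the point without removing it. The protocol itself fixes an unmasked review during conduct, adds an open-ended second component to the definition, and draws the sub-studies from the result.

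**Conclusion.** The concern holds in a limited form. Classification by staff who can see the cohort, on an open-ended criterion, allows error to differ by cohort. The exposed results are the per-cohort frequency of Long-COVID, the summaries by status, sub-study selection and contrasts pooled over cohorts. Contrasts within a cohort would mainly be weakened.

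Neither the sign nor the size can be known from the protocol. At an assumed true frequency of 30% and the error rates in Step 1, the spurious difference is about 3 to 15 points, against a half-width of about 13. In a descriptive study this is a weakness in how a key variable is formed. It is not evidence that the results will be wrong.

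**What to change.** Change section 4.1 and footnote 12 to a two-step assignment.

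1. Give every participant a provisional status by a pre-set rule (listed symptom items, onset relative to infection, duration). Apply it to an eCRF extract without the cohort, hospitalisation, ICU/oxygen, vaccination and test-type fields. Lock it before sub-study selection.
2. Where hospital history is needed to judge an alternative explanation, allow a second, unmasked step. Log each change with its reason.

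Report between-cohort results under both the locked and the final status, so that the effect of unmasked judgement on each cohort is visible.

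The cost is one extract, one written rule and a change log, using data and staff already in place. Masking will be partial: at a single centre staff may recognise participants, and the symptom-directed history is still taken by people who may know the cohort. A fixed rule limits the first problem but does not cure the second.
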